3.1 Primary and Secondary Outcome Measure for PK Component

- Maternal Steady state TFV-DP concentration levels at Week 12.

3.2 Primary Outcome Measure(s) for PrEP Comparison Component

PrEP adherence:

- TFV-DP drug concentration level in Dried Blood Spots (DBS)

Maternal Adverse Events:

- Maternal Grade 3 or higher adverse events (signs, symptoms, labs, and diagnoses)
- Maternal Grade 2 or higher chemistry abnormalities

Adverse Pregnancy Outcomes:

Composite outcome of

- Spontaneous abortion (occurring at <20 weeks gestation)
- Stillbirth (occurring at ≥ 20 weeks gestation)
- Preterm delivery (<37 completed weeks' gestation)
- Small for gestational age (<10th percentile using **INTERGROWTH-21st** norms and ultrasound derived gestational age at delivery)

Infant Safety:

Infant Adverse Events

- Infant death within the first 26 weeks of life
- Infant Grade 3 or higher adverse events (signs, symptoms, labs, diagnoses) reported between birth and 26 weeks postpartum

Infant Growth and Development

- Infant bone mineral content based on DXA scan of the whole body (WB-BMC) at birth and lumbar spine (LS-BMC) at birth and 26 weeks postpartum
- Infant creatinine and CrCl rate at birth and 26 weeks postpartum measured by Schwartz equation
- Infant length for age z-score at birth and 26 weeks postpartum

4 Definitions

Baseline

Maternal baseline is defined as the measurement on or closest to the study entry date, and infant baseline is defined as the measurement at birth. For the PrEP Comparison Component analyses characterizing the proportion with optimal adherence to PrEP among women in Cohort 2 who subsequently decide to initiate PrEP, baseline is defined as the date initiating PrEP.

Visit Windows for Analysis

All analyses summarizing or referring to data by visit week include a visit window around the applicable study visit week. For maternal antepartum study visit weeks 4, 8, and 12 the visit window is +/- 14 days. The visit window is +/- 21 days for antepartum visit weeks 24 and 36. The Labor and Delivery/Infant birth visit may occur as soon as possible after delivery through 21 days postpartum. The visit window is +/- 21 days for the maternal and infant 6- week postpartum, 14-week postpartum, and 26-week postpartum visits.

Analysis Sets

PK Component:

- **PK Adherence Set:** All maternal participants on PrEP, including those in Group 1 and those in Group 2

PrEP Comparison Component:

- **Adherence Set:** All maternal participants on PrEP, including those in Cohort 1 and those in Cohort 2 who later decide to formally initiate PrEP. All visits/periods where maternal participants are actively prescribed PrEP.
- **Maternal Safety Set:** All maternal participants in Cohort 1 or Cohort 2, starting at enrollment
- **Infant Safety Set:** All liveborn infants in Cohort 1 or Cohort 2, starting at birth

5 General Considerations – PrEP Comparison Component

The primary analyses to address the primary objectives of the PK Component and the PrEP Comparison Component are outlined below. For a more detailed description of the analyses to be conducted, please refer to the Analysis Implementation Plan (AIP).

Categorical variables will be summarized as N (%), with corresponding 95% confidence intervals where applicable. Continuous variables will be summarized with means and standard deviations, medians and IQR (Q1, Q3), as well as min, max.

Descriptive summaries:

PK Component: We will summarize and compare demographic and clinical characteristics at enrollment between maternal PK Component Group 1 (enrolled in pregnancy) and maternal PK

Component Group 2 (enrolled postpartum). We will use Fisher's exact test to estimate differences in proportions and t tests or Wilcoxon rank-sum tests (as appropriate) for continuous measures.

PrEP Comparison Component: Entry demographic, pregnancy, pregnancy history, psychosocial, sexual behavior and partner characteristics of women in Cohort 1 and Cohort 2 will be summarized and compared using chi square tests (or Fishers exact test as appropriate) for discrete variables and t-tests or Wilcoxon tests for continuous variables.

6 Estimands and Estimation

6.1 Primary Estimand PK Component:

Primary Objective 1: To determine the concentration of tenofovir diphosphate (TFV-DP) associated with adequate adherence to FTC/TDF among women observed ingesting daily oral PrEP during pregnancy and postpartum.	
Estimand description	Maternal Steady state TFV-DP concentrations at Week 12
Treatment	1. Daily oral PrEP (200 mg FTC/ 300 mg TDF) during pregnancy and/or postpartum administered through direct observation.
Target population	Analysis set
Women who are pregnant and test HIV-negative, are 16-24 years of age, enrolled during a singleton pregnancy at 14-24 weeks' gestation or postpartum within 6-12 weeks after delivery, and express willingness to take daily oral PrEP under direct observation for 12 weeks	PK Adherence set: Women initiating PrEP
Variable(s)	Outcome measure(s)
TFV-DP drug concentration level	1. TFV-DP drug concentration level from Dried Blood Spots (DBS) measured at week 12 among pregnant women 2. TFV-DP drug concentration level from Dried Blood Spots (DBS) measured at week 12 among postpartum women.
Handling of intercurrent events	Handling of missing data

 Discontinuation of PrEP: Only visits occurring prior to discontinuation of PrEP will be included. (While on treatment strategy) 	
Missing data could occur in the following situations:
 
 Missing visit(s) when DBS would have been collected Missing drug concentration results due to sample collection or processing issues. 
If a single specimen is missing at week 12, and a specimen is available at week 11, sensitivity analyses will be conducted including the results from the analysis of the 11-week specimen.

Population-level summary measure 
 Median and IQR TFV-DP concentration levels at Week 12 in pregnant and postpartum groups. 	Analysis approach 
In each of the two groups (antenpartum and postpartum groups), the median and IQR of steady state concentration (Css), defined as the TFV-DP concentration observed at week 12 corresponding to 6-7 day/week adherence ("optimal adherence"), will be calculated for each group. Predicted TFV-DP concentration levels for each maternal participant will be obtained using a population PK model, and descriptive statistics will be generated. The estimated steady-state TFV-DP concentration thresholds for optimal adherence during pregnancy and postpartum will be based on the 25th percentile for 7 doses per week.

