### *Evaluating risk-benefit ratio*

Side effects associated with FTC/TDF (Truvada®) include diarrhea, nausea, fatigue, headache and rash which are seen in about 10% of participants during the initiation of therapy (68). While these early symptoms are generally well-tolerated and dissipate over a few weeks, such side effects may be less tolerable for pregnant or postpartum women. For HIV-infected pregnant and postpartum women, such risks – including the adverse bone and renal effects of TDF – are offset by the significant health benefits of taking the drug as part of ART. However, the risk of adverse drug effects in relation to the potential HIV prevention benefits for HIV-uninfected women at increased risk for infections requires further evaluation.

Tenofovir is a highly-charged anion that does not readily permeate across epithelial barriers. The water soluble pro-drug administered by mouth, TDF, is well absorbed in the gut and is rapidly converted to the active form - tenofovir. While tenofovir is present in amniotic fluid and cord blood, there is low penetration of active drug from maternal blood into breastmilk and subsequently across the infant gut. Low blood-milk penetration and infant drug levels were recently confirmed in a prospective study of 50 HIV uninfected lactating women receiving 10 days of directly observed oral dosing with FTC/TDF PrEP (69). While more ready excretion of FTC into breastmilk was evident, infant plasma concentrations were 0.5% of levels expected from therapeutic dosing in infants. This suggests the risk of postnatal exposure to PrEP in breastfed infants is low.

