#### ***Adverse Events***

The following adverse events— inclusive of abnormal laboratory test results and clinical signs, symptoms, and diagnoses — will be entered into maternal adverse events eCRFs:

For the PK Component:

- All Grade 3 or higher adverse events

For the PrEP Comparison Component:

- All Grade 2 or higher adverse events

For both the PK Component and PrEP Comparison Component:

- All adverse events that lead to a change of study drug
- All complications and sequela of adverse pregnancy outcomes.
- All serious adverse events (SAEs) as defined in Version 2.0 of the Manual for Expedited Reporting of Adverse Events to DAIDS (DAIDS EAE Manual)

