6.3.2 Second Primary Estimand

Primary Objective 2: To assess the safety of FTC/TDF for PrEP during pregnancy and postpartum by comparing pregnancy outcomes and maternal and infant safety between cohorts.	
Estimand description	Incidence rate ratio of cumulative adverse events (AEs) up to 26 weeks postpartum among PrEP exposed vs. PrEP unexposed women
Treatment	
 1. Daily oral PrEP (200 mg FTC/ 300 mg TDF) throughout follow-up. 2. Enhanced adherence support, including SMS messaging and feedback of drug levels with tailored counseling. 3. Behavioral HIV risk reduction package
Target population	Analysis set
Women who are pregnant and HIV-uninfected, 16-24 years of age, with a confirmed singleton pregnancy of 32 weeks' gestation or less and who have access to a mobile phone and are able to receive and read SMS messages	Maternal Safety Set: all enrolled maternal participants
Variable(s)	Outcome measure(s)
Occurrence of at least one of the following maternal AEs up to 26 weeks postpartum 
 • Grade 3 or higher adverse events • Grade 2 or higher chemistry abnormalities 	Outcome measures as defined by the variables (graded according to the NIAID DAIDS Table for Grading the Severity of Adult and Pediatric Adverse Events). 
 • The start of person-time for the PrEP-exposed group is study entry for Cohort 1 and Cohort 2/Step 2 entry for Cohort 2; • The start of person-time for the PrEP unexposed group is study entry (for Cohort 2 only; person-time is censored when initiating PrEP for participants enrolled in Cohort 2/Step 2)
Handling of intercurrent events	Handling of missing data

 • Failure to start PrEP (in Cohort 1 or Cohort 2/Step 2) (Treatment policy strategy) • Premature discontinuation of PrEP (Treatment policy strategy) 	Participants who discontinue follow-up before the 26-week postpartum visit will have their outcome determined based on data available until the time of discontinuation (i.e., a participant who discontinued follow-up without a prior AE is assumed not to have an AE had they been observed for the intended duration).
Population-level summary measure	Analysis approach

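### Maternal Grade 2 clinical adverse events are recorded in both cohorts, but neither the protocol nor the Primary SAP plans to compare them between exposure groups

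*SAP*

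**What the plan says.** **Collection.** Protocol 7.2.1 sets the maternal eCRF threshold for the PrEP Comparison Component at "All Grade 2 or higher adverse events". For the PK Component it is Grade 3. In both components, "All adverse events that lead to a change of study drug" are also entered, as are serious events. Protocol 7.2 applies the adverse event definition to every participant from enrollment, whether or not she is exposed to drug, so Cohort 2 is covered.

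**Analysis.** SAP 3.2 lists two maternal outcomes: "Maternal Grade 3 or higher adverse events (signs, symptoms, labs, and diagnoses" and "Maternal Grade 2 or higher chemistry abnormalities". Protocol Table 5 lists the same two. The estimand in SAP 6.3.2 is the "Incidence rate ratio of cumulative adverse events (AEs) up to 26 weeks postpartum among PrEP exposed vs. PrEP unexposed women", and its variable is an event of Grade 3 or above or one of the "Grade 2 or higher chemistry abnormalities". The supplemental analyses there (by antepartum or postpartum period, by adherence level, and time to first event) keep the same events. Protocol Tables 6 and 7 contain no Grade 2 clinical outcome.

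**Expected side effects.** Protocol 1.2, under the risk-benefit heading, says the side effects of FTC/TDF "include diarrhea, nausea, fatigue, headache and rash which are seen in about 10% of participants during the initiation of therapy". It calls these early symptoms generally well tolerated and short-lived, but adds that they may be harder to bear in pregnancy or after delivery. Protocol 13.5.4 places gastrointestinal intolerance mainly in the first month.

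**The concern.** Primary objective 2.3.2 is to assess safety by comparing the cohorts. The events the protocol itself expects most often at PrEP start are tolerability symptoms. If these are mostly mild to moderate, a Grade 3 cut removes much of that signal, and the only Grade 2 events left in the comparison are laboratory chemistry results.

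Nausea, fatigue and headache are also common in pregnancy without PrEP, so a count in Cohort 1 alone is hard to interpret. Cohort 2 supplies the background rate. The component set its recording threshold one grade lower than the PK Component, and the planned analysis makes no use of the extra clinical data.

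Timing adds to this. The primary rate ratio runs from entry to 26 weeks postpartum, and none of the planned splits isolates the first weeks on drug.

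**Working it through.** **1. Recorded against compared (maternal, PrEP Comparison Component)**

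| Event type | Entered in eCRF | In a planned between-group comparison |
|---|---|---|
| Grade 3 or above, any kind | Yes | Yes |
| Grade 2 chemistry | Yes | Yes |
| Grade 2 clinical | Yes | No |
| Grade 1 clinical | Only if serious or drug-changing | No |

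The third row is the gap. The fourth limits what any fix can recover.

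**2. Reproducing the plan's own figure.** Protocol Table 10 gives 10% versus 23% as detectable with 80% power at alpha 0.05, with 100 women in Cohort 2 and 200 in Cohort 1. The test and its sidedness are not stated; I assume a two-sided pooled z-test.

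- Pooled rate = (200 × 0.23 + 100 × 0.10)/300 = 0.1867
- SE under no difference = √[0.1867 × 0.8133 × (1/200 + 1/100)] = 0.0477
- SE under the alternative = √[0.23 × 0.77/200 + 0.10 × 0.90/100] = 0.0423
- Power = Φ[(0.13 − 1.96 × 0.0477)/0.0423] = Φ(0.863) = 80.6%

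This agrees with the stated 80%, so the power inputs are not in dispute.

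**3. What a Grade 2 or higher comparison could show.** The documents give neither the grade split of the cited 10% nor a background rate, so all rates below are assumptions. Power is for the same test by exact enumeration of both binomials. The last column is 1.96 × √[p₁(1 − p₁)/200 + p₂(1 − p₂)/100], in percentage points.

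| Exposed | Unexposed | Power | 95% CI half-width |
|---|---|---|---|
| 10% | 2% | 78% | 5.0 |
| 15% | 5% | 77% | 6.5 |
| 20% | 10% | 61% | 8.1 |
| 30% | 20% | 46% | 10.1 |
| 10% | 5% | 29% | 6.0 |
| 15% | 10% | 21% | 7.7 |
| 25% | 20% | 15% | 9.9 |

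The range over these pairs is 15% to 78%. Only one more favourable case was looked at: a full ten-point excess, all Grade 2 or above, over a 2% background (12% versus 2%). It gives 89% by the formula in step 2. If half of a ten-point excess is Grade 2 or above, the same formula gives 43%, 30%, 21%, 17% and 15% at backgrounds of 2%, 5%, 10%, 15% and 20%.

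**4. What the planned Grade 3 cut would retain.** Suppose start-up effects occur in an extra 10% of exposed women and 5% to 20% of those effects reach Grade 3 (assumed). The excess left in the outcome is 0.10 × 0.05 = 0.5 points to 0.10 × 0.20 = 2 points. By the formula in step 2, power is then about 3% to 12% over backgrounds of 2% to 20%.

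**The case against.** Protocol and SAP agree on the Grade 3 cut, so this is not a contradiction or a calculation error, and collecting more than the primary outcome uses is not a fault in itself. That stands: the point concerns the scope of the analysis.

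A reader might infer that Grade 2 clinical events are never analysed. The documents do not support that. Adverse event tabulations go to the CMC (Protocol 9.3.2), and summaries for both groups go to the SMC (Protocol 9.3.3). SAP 1.1 defers table detail to the Analysis Implementation Plan and other outcomes to a separate SAP, and neither is available here. Still, the CMC tabulations are pooled across arms, the SMC summaries are for monitoring, and the Other and Exploratory outcome lists contain no such item. What can be said is that no comparison is planned in the protocol or the Primary SAP.

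The severity premise is also open to challenge. Symptoms described as well tolerated may be Grade 1 as readily as Grade 2, and Grade 1 events would still be missed. It follows that the common side effects cannot be said to be largely absent from the comparison, only likely to be under-represented.

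Tolerability is partly covered elsewhere. SAP 6.3.1 reports who stopped PrEP and why, adverse event rates are compared across adherence levels, and the interviews may ask about side effects. But stopping reasons have no unexposed comparator, and the adherence comparison keeps the same grade limit. On timing, antepartum results are also stratified by gestational age at enrollment. For women who enter late in pregnancy, that period is mostly early exposure, which softens the timing criticism but leaves the grade limit in place.

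Finally, Grade 2 nausea, fatigue and headache are subjective, and exposure is open-label and self-selected. This limits causal reading and must be stated.

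**Conclusion.** The gap is real but moderate. Maternal Grade 2 clinical events are required data in both cohorts and have no planned between-group comparison in the protocol or Primary SAP. The start-up symptoms expected in about 10% of users are therefore likely to be under-represented in the comparison that serves primary objective 2.3.2. By how much cannot be computed, because the grade split is not given.

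Two stronger readings should be resisted. One is that the report would declare PrEP safe: Protocol 9.2.1 says power for safety conclusions is limited and presents the estimates as descriptive. The other is that the trial has nearly 80% power for these symptoms. That holds only for favourable inputs, such as 10% versus 2% or 15% versus 5%. It falls to 29% for 10% versus 5% and to 15% for 25% versus 20%, and a low background is hard to assume for symptoms common in pregnancy. The value of the added analysis lies in an estimate with its interval. All these figures assume 200 versus 100 women and a two-sided 0.05 test. No dose or clinical management rule is in question.

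**What to change.** Add one pre-specified supplemental analysis to SAP 6.3.2, labelled descriptive:

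- The rate and proportion of women with any Grade 2 or higher clinical adverse event, and with any Grade 2 or higher gastrointestinal, headache, fatigue or rash event taken as one group, by PrEP exposure, with 95% confidence intervals.
- The first 8 weeks after study entry (Cohort 1 versus Cohort 2) shown separately from later time. Cohort 2 women who start PrEP are censored from unexposed time at that point, as SAP 6.3.2 already does.
- Adjustment for gestational age at entry.
- A stated limitation: symptom reporting is open-label, cohorts are self-selected, and Grade 1 events are not routinely captured.

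Keeping the symptoms as a single group limits multiplicity, and specifying the table before analysis avoids choosing symptoms after seeing the data. The 8-week window is a judgement: it spans the Week 4 and Week 8 visits and covers the first month named in Protocol 13.5.4.

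The cost is SAP wording, some event coding and one table from eCRF data already required. The primary outcomes and sample size do not change.
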